10 DATA COLLECTION, QUALITY CONTROL AND QUALITY ASSURANCE

The investigator is required to keep accurate records to ensure the conduct of the study is fully documented. The period of record retention should be consistent with the record retention policies of the sponsoring agency or applicable regulatory agencies. However, in certain instances, documents should be retained for a longer period if required by the applicable regulatory agency or by the National Institutes of Health.

The investigator will report all protocol deviations to DAIT and the SACCC per the instructions in the ACE Manual of Operations. The SACCC will forward reports of protocol deviations to the responsible DAIT/NIAID medical officer for review as specified in the ACE Manual of Operations.

The SACCC is responsible for regular inspection of the conduct of the trial, for verifying adherence to the protocol, and for confirming the completeness, consistency and accuracy of all documented data.

Data will be obtained from a variety of sources including, but not limited to laboratory notebooks, automated instrument output files, and clinical subject charts. Data from these source materials will be transmitted to the SACCC via one of two mechanisms. Data collected electronically at central laboratories will be transferred electronically directly from the laboratory to the SACCC using standard secure data transfer procedures. Data collected at the clinical sites will be transmitted to the SACCC using an internet-based remote data entry system. Clinical site personnel use an internet browser to key data into electronic CRFs (eCRFs); each eCRF page is submitted to the SACCC data server electronically as the page is completed. Univariate data validation tests are performed as the data are keyed. The central database, which resides on the SACCC server, is backed up nightly; backup tapes are saved in a secure, off-site location. At any time, authorized site personnel may log in to the remote data entry system, review and correct previously entered data, or key additional data. The data will be further validated per the study data validation plan via a series of computerized and manual edit checks, and all relevant data queries will be raised and resolved on an ongoing basis. Complete, clean data will be frozen to prevent further inadvertent modifications. All discrepancies will be reviewed and any resulting queries will be resolved with the investigators and amended in the database. All elements of data entry (i.e., time, date, verbatim text, and the person performing the data entry) will be recorded in an electronic audit trail to allow all data changes in the database to be monitored and maintained in accordance with federal regulations.

The SACCC will periodically visit the participating clinical sites and audit the source documents in order to validate the data in the SACCC central database. Data will be provided using the subject's screening or enrollment number; the SACCC will not collect personally identifying information such as the subject's name or social security number. Subjects will provide demographic information such as race, ethnicity, and birth date.

Data collected by the SACCC will be held in the strictest confidence, and are protected from access that could reveal personally identifying information about any subject in the trial.

11 ETHICAL CONSIDERATIONS AND COMPLIANCE WITH GOOD CLINICAL PRACTICE

The study will be conducted according to Good Clinical Practice (GCP) guidelines, U.S. 21 CFR Part 50 – Protection of Human Subjects, and Part 56 – Institutional Review Boards.

11.1 Compliance with Good Clinical Practices

This trial will be conducted in compliance with the protocol, current GCPs recommended by the International Conference on Harmonization (ICH) and the applicable regulatory requirements for participating institutions. These include the tenets of the Declaration of Helsinki and review and approval by the appropriate ethics review committee or IRBs of participating organizations. The SACCC will assure compliance through a program of quality assurance audits performed both at participating sites and within the SACCC for data quality and adherence to protocol requirements. The SACCC is operated by Rho Federal Systems Division, Inc. (RhoFED), Chapel Hill, North Carolina under a contract from DAIT/NIAID.

11.2 Institutional Review Board

Each participating institution must provide for the review and approval of this protocol and associated informed consent documents by an appropriate ethics review committee or IRB. Any amendments to the protocol or consent materials must be approved by the IRB and submitted to the FDA before they are placed into use. In both the United States and in other countries, only institutions holding a current Federal Wide Assurance issued by the Office of Human Research Protection (OHRP) at the Department of Health and Human Services (DHHS) may participate.

The investigator will inform the IRB of serious or unexpected AEs that might occur during the study and are likely to affect the safety of the subjects, or the conduct of the study. The investigators will comply fully with all IRB requirements for both the reporting of AEs, protocol or consent form changes, as well as any new information pertaining to the use of the study medication that might affect the conduct of the study.

11.3 Informed Consent

The principles of informed consent in the current edition of the Declaration of Helsinki, as well as compliance with all IRB requirements, will be implemented in the study, before any protocol-specified procedures are carried out. A standard consent form for subject participation will be provided with the protocol to each institution. Any modifications to the

standard information in the template will require review and approval by the SACCC and DAIT/NIAID. Informed consent will be obtained in accordance with 21 CFR 50.52. Information may be given to subjects in oral, written or video form by the investigator. All prospective subjects will be given ample time to read the consent form, and ask questions, before signing.

If subjects are to be enrolled who do not speak and read English, the consent materials must be translated into the language appropriate for the enrolling subject. Translated documents must be certified to contain the complete descriptions provided in the English version of the document. If an interpreter is used to provide or assist in describing the consent materials to an enrolling subject, the interpreter must also sign the consent materials certifying their involvement with the consent process.

After completion, a copy of the signed consent form will be given to the subject. The original signed consent form will be kept on file in the subject's study chart, available for inspection by regulatory authorities, both federal and institutional.

11.4 Data and Safety Monitoring Board

The responsibility for reviewing the ethical conduct of the study and for monitoring reports of evidence of adverse or beneficial effect is assigned to the DAIT Autoimmunity Data and Safety Monitoring Board (DSMB). The DSMB is an independent group composed of biomedical ethic experts, physicians, and other scientists who are responsible for continuing review of study information. The DSMB makes recommendations to DAIT/NIAID on issues affecting the course and conduct of this clinical study.

12 FINANCING AND INSURANCE

Participating institutions must comply with their institution's policies on compensation, insurance, and indemnity. Institutions must have adequate liability insurance coverage to satisfy their local and national requirements for study participation.

13 PUBLICATION POLICY

The Autoimmunity Centers of Excellence (ACE) policy on publication of study results will apply to this study. Authorized participants may find details regarding the policy statement on the ACE internet website at <http://www.rhoworld.com>. Study investigators are encouraged to communicate and publish study results with prior notification of DAIT/NIAID and Genentech, Inc. The following procedure is suggested:

1. Manuscripts, abstracts, posters and other material for public distribution will be submitted to DAIT/NIAID, and Genentech, Inc. at least 30 days prior to submission for publication or public presentation.
2. DAIT/NIAID, and Genentech, Inc. will review and comment on the proposed material within 30 days.
3. DAIT/NIAID, and/or Genentech, Inc. may ask that confidential information be deleted or redacted in this case where a patent may be filed or where confidential

information is involved. Publication or presentation may be delayed up to 60 additional days in order to file a patent application.

15 APPENDICES

Appendix A: Modified Scleroderma Health Assessment Questionnaire (SHAQ)

Appendix B: Short Form – 36 Health Survey (SF-36)

Appendix C: New York Heart Association Classification of Heart Disease

Appendix D: Subject Self-Reported Demographics Source Document

Appendix E: Exploratory Analysis: Standardized Fick-based Pulmonary Vascular Resistance and Pulmonary Artery Capacitance

Appendix F: RESTORE Sub-study Protocol

15.1 Appendix A: Modified Scleroderma Health Assessment Questionnaire (SHAQ)

Page 1 of 2

Modified Scleroderma Health Assessment Questionnaire (SHAQ)

Subject ID: _____ Date (MM/DD/YY): ____/____/____

In the past seven (7) days,	Without any difficulty	With some difficulty	With much difficulty	Unable to do
1. Are you able to: Dress yourself, including tying shoelaces and doing buttons? Shampoo your hair?				
2. Are you able to: Stand up from an armless straight chair? Get in and out of bed?				
3. Are you able to: Cut your meat? Lift a full cup or glass to your mouth? Open a new carton of milk?				
4. Are you able to: Walk outdoors on flat ground? Climb up 5 steps?				
5. Are you able to: Wash and dry your entire body? Take a tub bath? Get on and off the toilet?				
6. Are you able to: Reach and get down a 5 pound object (such as a bag of sugar) from just above your head? Bend down and pick up clothing from the floor?				
7. Are you able to: Open car doors? Open jars which have previously opened? Turn regular taps on and off?				
8. Are you able to: Run errands and shop? Get in and out of a car? Do chores such as vacuuming or yard work?				

Page 2 of 2

Please check any Aids or Devices that you usually use:

Cane		Dressing Device (button hook, long shoe horn, etc)	
Walker		Built up / Special Utensils	
Bathub seat		Long Handled Appliances for reach	
Bathroom Bar		Long Handled Appliances for Bathroom	
Jar Opener		Raised Toilet seat	
Crutches		Special or Built-up Chair	
Wheelchair		Other (Specify)	

Please check any categories for which you usually need help from another person:

Hygiene		Gripping and Opening Things	
Reach		Errands and Chores	
Arising		Dressing and Grooming	
Eating		Walking	

Place a mark on the line to indicate the severity of the pain.

1. How much pain have you had because of your illness in the past week?

0 No pain 100 Very severe pain

2. In the past week, how much has your Raynaud's Phenomenon interfered with your activities?

Does not interfere Very severe limitation

3. In the past week, how much has/have your finger ulcer(s) interfered with your activities?

Does not interfere Very severe limitation

4. In the past week, how much have your intestinal problems interfered with your activities?

Does not interfere Very severe limitation

5. In the past week, how much have your breathing problems interfered with your activities?

Does not interfere Very severe limitation

6. Overall, considering how much pain, discomfort, limitations in your daily life and other changes in your body and life, how severe would you rate your disease today?

No disease Very severe

15.2 Appendix B: Short Form – 36 Health Survey (SF-36)

Autoimmune Centers of Excellence ARA05: Switching Anti-TNF to Agents in RA

SAMPLE

Subject Source Documentation for the Short Form-36 (SF-36)

Subject ID #: _____

Subject instructions:
Please complete the survey and return it to your ARA05 Study Coordinator. Please initial and date this form as indicated.

Subject initials: _____ Date survey completed: _____

Appendix E: Required Source Document Worksheets
SF-36

23 February 2007

SAMPLE

Your Health and Well-Being

This survey asks for your views about your health. This information will help keep track of how you feel and how well you are able to do your usual activities. *Thank you for completing this survey!*

For each of the following questions, please mark an in the one box that best describes your answer.

1. In general, would you say your health is:

Excellent	Very good	Good	Fair	Poor
				

2. Compared to one year ago, how would you rate your health in general now?

Much better now than one year ago	Somewhat better now than one year ago	About the same as one year ago	Somewhat worse now than one year ago	Much worse now than one year ago
				

SF-36™ Health Survey © 1996, 2000 by QualityMetric Incorporated and Medical Outcomes Trust. All Rights Reserved. SF-36® is a registered trademark of Medical Outcomes Trust. (SF-36v2 Standard, US Version 2.0)

SAMPLE

3. The following questions are about activities you might do during a typical day. Does your health now limit you in these activities? If so, how much?

	Yes, limited a lot	Yes, limited a little	No, not limited at all
	▼	▼	▼

- Vigorous activities, such as running, lifting heavy objects, participating in strenuous sports
- Moderate activities, such as moving a table, pushing a vacuum cleaner, bowling, or playing golf
- Lifting or carrying groceries
- Climbing several flights of stairs
- Climbing one flight of stairs
- Bending, kneeling, or stooping
- Walking more than a mile
- Walking several hundred yards
- Walking one hundred yards
- Bathing or dressing yourself

SF-36™ Health Survey © 1996, 2000 by QualityMetric Incorporated and Medical Outcomes Trust. All Rights Reserved. SF-36® is a registered trademark of Medical Outcomes Trust. (SF-36v2 Standard, US Version 2.0)

SAMPLE

4. During the **past 4 weeks**, how much of the time have you had any of the following problems with your work or other regular daily activities as a result of your physical health?

All of the time	Most of the time	Some of the time	A little of the time	None of the time
-----------------	------------------	------------------	----------------------	------------------

Cut down on the **amount of time** you spent on work or other activities.....
 Accomplished less than you would like.....
 Were limited in the **kind** of work or other activities.....
 Had **difficulty** performing the work or other activities (for example, it took extra effort).....

5. During the **past 4 weeks**, how much of the time have you had any of the following problems with your work or other regular daily activities as a result of any **emotional problems** (such as feeling depressed or anxious)?

All of the time	Most of the time	Some of the time	A little of the time	None of the time
-----------------	------------------	------------------	----------------------	------------------

Cut down on the **amount of time** you spent on work or other activities.....
 Accomplished less than you would like.....
 Did work or other activities **less carefully than usual**.....

SF-36™ Health Survey © 1996, 2000 by QualityMetric Incorporated and Medical Outcomes Trust. All Rights Reserved. SF-36® is a registered trademark of Medical Outcomes Trust. (SF-36® Standard, US Version 2.0)

SAMPLE

6. During the **past 4 weeks**, to what extent has your physical health or emotional problems interfered with your normal social activities with family, friends, neighbors, or groups?

Not at all	Slightly	Moderately	Quite a bit	Extremely
------------	----------	------------	-------------	-----------

7. How much **bodily pain** have you had during the **past 4 weeks**?

None	Very mild	Mild	Moderate	Severe	Very Severe
------	-----------	------	----------	--------	-------------

8. During the **past 4 weeks**, how much did **pain** interfere with your normal work (including both work outside the home and housework)?

Not at all	A little bit	Moderately	Quite a bit	Extremely
------------	--------------	------------	-------------	-----------

SF-36™ Health Survey © 1996, 2000 by QualityMetric Incorporated and Medical Outcomes Trust. All Rights Reserved. SF-36® is a registered trademark of Medical Outcomes Trust. (SF-36® Standard, US Version 2.0)

SAMPLE

9. These questions are about how you feel and how things have been with you during the **past 4 weeks**. For each question, please give the one answer that comes closest to the way you have been feeling. How much of the time during the **past 4 weeks**...

All of the time	Most of the time	Some of the time	A little of the time	None of the time
-----------------	------------------	------------------	----------------------	------------------

Did you feel full of life?
 Have you been very nervous?
 Have you felt so down in the dumps that nothing could cheer you up?
 Have you felt calm and peaceful?
 Did you have a lot of energy?
 Have you felt downhearted and depressed?
 Did you feel worn out?
 Have you been happy?
 Did you feel tired?

10. During the **past 4 weeks**, how much of the time has your **physical health or emotional problems** interfered with your social activities (like visiting friends, relatives, etc.)?

All of the time	Most of the time	Some of the time	A little of the time	None of the time
-----------------	------------------	------------------	----------------------	------------------

SF-36™ Health Survey © 1996, 2000 by QualityMetric Incorporated and Medical Outcomes Trust. All Rights Reserved. SF-36® is a registered trademark of Medical Outcomes Trust. (SF-36® Standard, US Version 2.0)

SAMPLE

11. How **TRUE** or **FALSE** is each of the following statements for you?

Definitely true	Mostly true	Don't know	Mostly false	Definitely false
-----------------	-------------	------------	--------------	------------------

I seem to get sick a little easier than other people.....
 I am as healthy as anybody I know.....
 I expect my health to get worse.....
 My health is excellent.....

THANK YOU FOR COMPLETING THESE QUESTIONS!

SF-36™ Health Survey © 1996, 2000 by QualityMetric Incorporated and Medical Outcomes Trust. All Rights Reserved. SF-36® is a registered trademark of Medical Outcomes Trust. (SF-36® Standard, US Version 2.0)

15.3 Appendix C: New York Heart Association Classification of Heart Disease

Functional Capacity	Objective Assessment
Class I. Patients with cardiac disease but without resulting limitation of physical activity. Ordinary physical activity does not cause undue fatigue, palpitation, dyspnea, or anginal pain.	A. No objective evidence of cardiovascular disease.
Class II. Patients with cardiac disease resulting in slight limitation of physical activity. They are comfortable at rest. Ordinary physical activity results in fatigue, palpitation, dyspnea, or anginal pain.	B. Objective evidence of minimal cardiovascular disease.
Class III. Patients with cardiac disease resulting in marked limitation of physical activity. They are comfortable at rest. Less than ordinary activity causes fatigue, palpitation, dyspnea, or anginal pain.	C. Objective evidence of moderately severe cardiovascular disease.
Class IV. Patients with cardiac disease resulting in inability to carry on any physical activity without discomfort. Symptoms of heart failure or the anginal syndrome may be present even at rest. If any physical activity is undertaken, discomfort is increased.	D. Objective evidence of severe cardiovascular disease

The Criteria Committee of the New York Heart Association. Nomenclature and Criteria for Diagnosis of Diseases of the Heart and Great Vessels. 9th ed. Boston, Mass: Little, Brown & Co; 1994:253-256.

15.4 Appendix D: Subject Self-Reported Demographics Source Document

Subject ID #: ____-____-____

Subject instructions: Please complete the survey by checking the box or boxes that most closely identify your race and ethnicity. Check multiple boxes if necessary. Initial and date this form as indicated and return it to your ASC01 Study Coordinator.

Date of Birth: _____ MM / DD / YYYY	Gender:  Male  Female
---	--

Ethnicity: Hispanic or Latino Not Hispanic or Latino

Race:

White:	Asian:
 White, not otherwise specified	 Asian, not otherwise specified
 Eastern European	 Asian Indian/South Asian
 European, not otherwise specified	 Chinese
 Mediterranean	 Filipino
 Middle Eastern	 Guamanian
 North Coast of Africa	 Korean
 Western European	 Japanese
 White Caribbean	 Vietnamese
 White North American	 Other Southeast Asian
 White South or Central American	
	Native Hawaiian or Other Pacific Islander:
Black or African American:	 Hawaiian
 Black, not otherwise specified	 Native Pacific Islander, not otherwise specified
 African American	 Samoan
 African Black (both parents born in Africa)	
 Caribbean Black	American Indian or Alaska Native:
 South or Central America Black	 Native American, not otherwise specified
	 American Indian, not otherwise specified
Other:	 Caribbean Indian
 No response	 Native Alaskan/Eskimo/Aleut
 Unknown	 South or Central American Indian
 Other, specify:	

Subject Initials: _____ Date survey completed: _____

15.5 Appendix E: Exploratory Analysis: Standardized Fick-based Pulmonary Vascular Resistance and Pulmonary Artery Capacitance

Standardized Fick-based pulmonary vascular resistance (PVR_f, in Woods Units) and pulmonary artery capacitance (PAC_f, in mL/mmHg) are calculated as follows:

$$PVR = TPG / CO$$

where TPG = Transpulmonary Gradient (mmHg)
CO = Cardiac Output (L/min)

$$TPG = mPAP - PCWP$$

where mPAP = mean pulmonary artery pressure (mmHg)
PCWP = mean pulmonary capillary wedge pressure (mmHg)

Thus, the Fick-based calculation of PVR is:

$$PVR_f = (mPAP - PCWP) / CO_f$$

where CO_f = Fick cardiac output (L/min)

$$CO_f = VO_2 / ((Ca - Cv) \times cHb \times 13.6)$$

where VO₂ = oxygen consumption according to LaFarge and Meittinen (mL/min)[161]

Ca = arterial oxygen saturation (%) (systemic)
Cv = venous oxygen saturation (%) (pulmonary artery)
cHb = hemoglobin concentration (g/L)

$$VO_2(\text{males}) = (138.1 - 11.49 \ln \text{Age} + 0.378 \text{ HR}) \times \text{BSA}$$

$$VO_2(\text{females}) = (138.1 - 17.04 \ln \text{Age} + 0.378 \text{ HR}) \times \text{BSA}$$

where lnAge = natural log of age in years
HR = heart rate (beats/min)
BSA = body surface area (m²)

The DuBois and DuBois formula is used to calculate body surface area.

$$BSA (m^2) = 0.20247 \times \text{Height}(m)^{0.725} \times \text{Weight}(kg)^{0.425}$$

Pulmonary artery capacitance is calculated as follows.

$$PAC_f = SV_f / PP$$

where SV = stroke volume (mL)
PP = pulse pressure (mmHg)

$$SV_f = CO_f \times 1000 / HR$$

$$PP = \text{systolic PAP} - \text{diastolic PAP}$$

where PAP is the pulmonary artery pressure

15.6 Appendix F: RESTORE Sub-study Protocol**Sub-study Protocol Title: Right Ventricular Response to Rituximab in Systemic Sclerosis-Assoiated Pulmonary Arterial Hypertension – A Magnetic Resonance Imaging Sub-study****Short Title: RESTORE Sub-Study****RESTORE Sub-study Sponsor:****VERA MOULTON WALL CENTER FOR PULMONARY VASCULAR DISEASE,
STANFORD UNIVERSITY****RESTORE Protocol Chair:**

[name]
Stanford University School of Medicine
Division of Pediatric Cardiology
[name]
Palo Alto, CA 94304-5731
[contact]
[contact]
Email: [contact]

RESTORE Protocol Co-Chairs:

[name], FCCP
Stanford University School of Medicine
Vera Moulton Wall Center for Pulmonary
Vascular Disease
Division of Pulmonary & Critical Care Medicine
[name]
Stanford, Ca 94305
[contact]
[contact]
E-mail: [contact]

[name], MPH
Lucile Packard Children's Hospital
Vera Moulton Wall Center for Pulmonary
Vascular Disease
Division of Pediatric Cardiology
[name]
Palo Alto, CA 94304-5731
[contact]
[contact]
E-mail: [contact]

Sub-study Protocol Synopsis

Title of Sub-study Protocol: Right Ventricular Response to Rituximab in Systemic Sclerosis Associated Pulmonary Arterial Hypertension – A Magnetic Resonance Imaging Sub-study (RESTORE Sub-Study)

Investigators: [name]; [name], FCCP; [name], MPH

Objectives:

The primary objective of the RESTORE sub-study is to evaluate the therapeutic effect of rituximab on the right ventricle (RV) in patients with SSc-PAH. Changes in right ventricular end diastolic volume index (RVEDVI) and stroke volume (SV) determined by cardiac MRI will be used as surrogates of RV function and prognosis. We hypothesize that RVEDVI and SV will reduce 24 weeks following rituximab therapy as compared to the placebo control.

Criteria for Evaluation:

All cardiac MRI (CMRI) endpoints will be assessed at baseline and at the Week 24 follow-up (or at time of discontinuation from the study) in 20 patients from each arm (80 studies total). The change in RVEDVI, RV mass, and SV will be analyzed and compared between placebo and rituximab cohorts. These sub-study endpoints will be used to augment the hemodynamic findings of the main study (ASC01). It is likely that comparison between hemodynamic response and surrogates of RV function by cardiac MRI will be valuable. Correlation of hemodynamic and CMRI parameters may allow for further determination of mechanisms of therapeutic effect of rituximab in this study.

Study Design:

Enrollment for the RESTORE sub-study will parallel that of the ASC01 protocol. The sub-study will enroll patients who have consented for the primary clinical study across all centers that participate in the RESTORE sub-study. The sub-study is designed to compare 20 rituximab with 20 placebo treated patients at baseline and at the Week 24 follow up. All ASC01 study inclusion and exclusion criteria apply. Furthermore, there are additional exclusion criteria that pertain only to the RESTORE sub-study: 1) known hypersensitivity to Gadolinium, 2) inability to tolerate or cooperate with MRI, 3) morbid obesity, and 4) presence of metallic objects or pacemakers.

Efficacy Endpoints:

The primary efficacy endpoint will be change in RVEDVI measured by cardiac MRI from baseline to 24 weeks after treatment initiation.

The secondary efficacy endpoints will be as follows:

1. Change in RV mass measured by cardiac MRI from baseline to 24 weeks after treatment initiation.
2. Change in SV measured by cardiac MRI from baseline to 24 weeks after treatment initiation.

Images and Analyses:

Cardiac MR imaging will be performed on any 1.5 T scanner (standard clinical equipment will meet these specifications) with simultaneous ECG recording. Image acquisition is based on routine MR protocols for traditional volumetric parameters supplemented with a delayed enhancement perfusion protocol (gadolinium). The detailed MRI protocol is specified in the Manual of Procedures (MOP), but will include short axis and four chamber views of the heart, and MRI angiography in the pulmonary artery and aorta. This will be followed by contrast enhanced imaging using gadolinium to determine myocardial perfusion in a four chamber view, and to evaluate for late enhancement using four chamber and short axis views.

Image analysis will be carried out off-line by investigators at Stanford University who are blinded to treatment arm, using validated MRI software tools such as QMass/QFlow (Medis Medical Imaging Systems, Raleigh, NC).

Sample Size and Statistical Analyses:

This sub-study will include 20 subjects treated with rituximab and 20 subjects treated with placebo.

The primary efficacy analysis of change in RVEDVI from baseline to 24 weeks will be performed on the intention-to-treat (ITT) population. Analysis of covariance (ANCOVA) will be used to model baseline to Week 24 change in RVEDVI as the primary outcome and treatment as the primary predictor, controlling for center and baseline value of RVEDVI.

Secondary analyses will include repeating the primary analysis for the following outcomes: change in RV mass from baseline

to 24 weeks and change in SV from baseline to 24 weeks.

1 Hypothesis

Primary Hypothesis: Right ventricular end-diastolic volume index (RVEDVI), as determined by cardiac MRI, will reduce 24 weeks following rituximab therapy as compared to placebo control, in subjects with SSc-PAH participating in ACE Protocol ASC01.

Secondary Hypotheses:

- Right ventricular mass, as determined by cardiac MRI, will reduce 24 weeks following rituximab therapy as compared to placebo control, in subjects with SSc-PAH participating in ACE Protocol ASC01.
- Stroke volume, as determined by cardiac MRI, will reduce 24 weeks following rituximab therapy as compared to placebo control, in subjects with SSc-PAH participating in ACE Protocol ASC01.

Exploratory Hypotheses:

- Cardiac output, as determined by cardiac MRI, will agree with the main study assessment of cardiac output as well as the standardized Fick-based calculation of cardiac output
- Right ventricular end diastolic volume, as determined by cardiac MRI, will correlate with the standardized Fick-based calculation of pulmonary artery capacitance

2 Background and Rationale

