 29. Laboratory parameters at the screening visit showing any of the following abnormal results:
 - Transaminases > 2x the upper limit of normal (ULN) and/or bilirubin > 2x ULN.
 - Absolute neutrophil count (ANC) < 1,500/mm³ (or < 1.5 x 10⁹/L).
 - Platelet count < 100,000/mm³ (or < 100 x 10⁹/L).
 - Hemoglobin < 9 g/dL.
 30. Concurrent treatment in a clinical research study using a non-FDA approved agent, with the exception of an open-label study/study extension of investigational prostanoids, endothelin receptor antagonists, PDE-5 inhibitors, and guanylate cyclase stimulators, provided the open-label investigational drug will be available and dose will remain stable through the ASC01 primary endpoint time point of 24 weeks after randomization in ASC01.
 31. Any condition or treatment, which in the opinion of the investigator, places the subject at unacceptable risk as a participant in the trial.

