8.3.4 Exploratory Analysis

Agreement between a secondary endpoint (PVR calculated by site-based standards) and the standardized Fick-based calculation of PVR (PVR_f) will be assessed using the method of Bland and Altman, separately for baseline and Week 24 right heart catheterization. Analyses will also be subset on method of calculation of cardiac output (thermodilution vs. Fick) if found to be a significant predictor in the ANCOVA model.

This secondary efficacy analysis will be repeated for PVR_f. Change from baseline in the standardized Fick-based calculation of pulmonary artery capacitance (PAC_f) will also be analyzed in the same manner as the PVR efficacy analysis.

Additionally, the relationship between change in PVR and change in 6MWD at Week 24 will be analyzed using a Spearman's rank correlation coefficient. Relationships between additional clinical outcomes and 6MWD or PVR can also be provided. These clinical outcomes will be addressed in the SAP.

The analyses of Treatment Satisfaction responses will also be considered exploratory. Questions will include:

1. Do you think you benefited by being in the study?
2. Have you noticed any long term benefits from study treatment?
3. Do you think you received rituximab or placebo?

All exploratory analyses will be conducted on subjects in the ITT population with available data.

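### The Appendix E Fick cardiac-output formula is inconsistent with its own units: 1,000-fold wrong as printed, and tenfold wrong if saturations are entered as fractions

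*Protocol*

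**What the plan says.** Appendix E of the protocol (15.5) gives the only formula in either document for the standardized Fick quantities:

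- `CO_f = VO2 / ((Ca − Cv) × cHb × 13.6)`, with the result labelled "CO_f = Fick cardiac output (L/min" per the legend and VO2 in mL/min.
- The saturations are "Ca = arterial oxygen saturation (%) (systemic" and "Cv = venous oxygen saturation (%) (pulmonary artery", so both are in percent.
- Haemoglobin is "cHb = hemoglobin concentration (g/L", so it is in grams per litre.
- `PVR_f = (mPAP − PCWP) / CO_f`, in Wood units.
- `PAC_f = SV_f / PP`, with `SV_f = CO_f × 1000 / HR`, in mL/mmHg.

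There is no division by 100 for the percentages and no conversion from g/L to g/dL. Elsewhere the protocol gives haemoglobin per decilitre: the laboratory exclusion in section 4.2 reads "Hemoglobin < 9 g/dL".

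The results are used in Protocol 8.3.4, where agreement between site-calculated PVR and PVRf "will be assessed using the method of Bland and Altman, separately for baseline and Week 24 right heart catheterization". The PVR efficacy analysis is then repeated for PVRf and for PACf. The RESTORE sub-study (Appendix F, sections 1 and 5) hypothesizes that MRI cardiac output agrees with the Fick output and that right ventricular volume correlates with PACf.

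The SAP synopsis only refers back to Appendix E. SAP 7.3.1 derives PVR from the recorded cardiac output, and SAP section 11 lists no change to the Fick formula.

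**The concern.** The constant and the unit labels cannot all be right. Oxygen carried per litre of blood is haemoglobin per litre, times oxygen capacity per gram, times saturation as a fraction. The constant 13.6 already contains a tenfold conversion from decilitres to litres. Using it with haemoglobin per litre applies that conversion twice, and entering saturations as whole percentages adds a further factor of 100.

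Three of the four exploratory objectives in Protocol 2.3 depend on PVRf or PACf: agreement with site PVR, sensitivity of the PVR result to standardization, and capacitance as an endpoint. An agreement analysis between two measures on different scales says nothing about agreement. Anyone who notices the fault while programming must also guess which label to change. Correcting only the percentages leaves a tenfold error.

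**Working it through.** The documents report no value of CO_f, PVRf or PACf to reproduce. The check is therefore a unit analysis, a worked patient, and a comparison with the protocol's own PVR figures.

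**Unit analysis.** Read 13.6 as 1.36 mL oxygen per g haemoglobin × 10 dL/L. This reading is an assumption; the documents do not explain the constant. The consistent denominator is (fractional saturation difference) × (Hb in g/dL) × 13.6. Relative to that:

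- saturations in percent multiply the denominator by 100;
- haemoglobin in g/L multiplies it by 10;
- together, 100 × 10 = 1,000.

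The ratio does not depend on the patient. If the capacity behind the constant is taken as 1.34 to 1.39 mL/g, the factor is 13.6 × 100 / 1.34 = 1,015 to 13.6 × 100 / 1.39 = 978.

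**Worked patient.** All values are assumed: woman, 60 years, 1.63 m, 70 kg, heart rate 80, saturations 95% and 65%, Hb 13 g/dL = 130 g/L, transpulmonary gradient 35 mmHg, pulmonary pulse pressure 42 mmHg. With the Appendix E equations:

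- BSA = 0.20247 × 1.63^0.725 × 70^0.425 = 1.755 m²
- VO2 = (138.1 − 17.04 × ln 60 + 0.378 × 80) × 1.755 = 173 mL/min
- As printed: CO_f = 173 / (30 × 130 × 13.6) = 173 / 53,040 = 0.00326 L/min
- Consistent units: CO_f = 173 / (0.30 × 13 × 13.6) = 173 / 53.04 = 3.26 L/min

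| Saturation and Hb units, with 13.6 | CO_f (L/min) | PVRf = 35/CO_f (Wood units) | PACf = CO_f × 1000/80/42 (mL/mmHg) |
|---|---|---|---|
| %, g/L (as printed) | 0.00326 | 10,729 | 0.00097 |
| %, g/dL | 0.0326 | 1,073 | 0.0097 |
| fraction, g/L | 0.326 | 107 | 0.097 |
| fraction, g/dL | 3.26 | 10.7 | 0.97 |

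CO_f and PACf are too small and PVRf too large, by the same factor.

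**Comparison with the protocol's own figures.** Entry requires PVR above 3 Wood units (Protocol 4.1). Mean baseline PVR was about 553 dyne (Protocol 8.1), which is 553 / 80 = 6.9 Wood units at 80 dyne units per Wood unit. Over a wide assumed grid (both sexes, age 18–75, heart rate 60–110, three body sizes from 1.5 m and 45 kg to 1.85 m and 110 kg, Hb 9–17 g/dL, saturation difference 15–40 points, gradient 15–50 mmHg), PVRf ranges:

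- as printed: 806 to 38,700 Wood units;
- fractions with g/L: 8.1 to 387;
- consistent units: 0.8 to 38.7.

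Only the consistent version spans the trial's values. The other conversions in Appendix E, the BSA constant for height in metres and the 1000 in stroke volume, are correct. The fault lies only in the cardiac-output line.

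**The case against.** **Much of the effect cancels.** A constant multiplier applied to every subject at both visits drops out of percent change, correlations, and the p-value for a treatment difference. The between-arm tests on PVRf and PACf, and the RESTORE correlation of right ventricular volume with PACf, would be unchanged. This stands and limits the damage to agreement analyses and reported absolute values, including the size of any treatment difference in PVRf or PACf. It holds only if every subject has the same unit error. SAP 8.4 says haematology came from local laboratories for subjects randomized before March 19, 2013 and from a central laboratory afterwards, with conversion to standardized units where possible. If those values supply cHb, which the documents do not say, the factor could differ between subjects and would then not cancel.

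**The percent sign could mean hundredths.** On that reading 95% − 65% = 0.30, and only the tenfold haemoglobin error remains. This is a fair alternative, and it still leaves the formula wrong.

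**It may be a label slip that shows itself.** Haemoglobin is in g/dL elsewhere, so a lost letter is possible, and a cardiac output of 0.003 L/min would stop any programmer. A 1,000-fold error probably would be noticed. A tenfold one is less certain for individual subjects: the low end of the grid, 8.1 Wood units, looks ordinary in this population, although the group mean would not.

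**Reach is small.** The SAP specifies no PVRf or PACf analysis beyond its synopsis, and RESTORE section 8.3 gives no method for the MRI-versus-Fick comparison. Both are true. Protocol 8.3.4 and Appendix E remain the governing text for these analyses.

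**Conclusion.** The concern holds. With the units as stated, the Appendix E formula understates cardiac output and PACf by a factor of 1,000 and overstates PVRf by 1,000. With fractional saturations the factor is 10. The sizes rest on reading 13.6 as 1.36 × 10, and the protocol's own PVR values confirm the order of magnitude. The patient values in the example are assumed, but the ratio does not depend on them.

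Followed literally, the agreement analysis of site PVR with PVRf and the agreement of MRI with Fick cardiac output would be uninterpretable, and absolute PVRf and PACf results would be wrong. The primary 6MWD analysis and the secondary analysis of site-based PVR are not affected. This should be corrected, but it does not threaten the main conclusions of the trial.

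**What to change.** Amend the cardiac-output line in Appendix E in one of two equivalent ways:

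- define Ca and Cv as fractions and cHb in g/dL, and keep 13.6; or
- keep percent and g/L, and replace 13.6 with 0.0136. For the example, 30 × 130 × 0.0136 = 53.04, the same denominator as 0.30 × 13 × 13.6.

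In the derivation program, confirm the unit of each haemoglobin value before use and add a range check on the derived cardiac output, so that a value wrong by a factor of 10 or more is queried. The cost is a one-line correction to the appendix and the matching line of code. No new data are needed.
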